5.0 Study Calendar

	Screening	Baseline	Weekly Coaching Sessions 1-4	3-Month Follow-up^
Informed Consent and Authorization	X			
Eligibility Checklist	X			
Demographics, Contact Information	X			
PAM-MH		X		X
ACE Measure		X		X
PEPPI-5		X		X
IMR Scale		X		X
RAS		X		X
NEII				X
Intervention**			X	

[^]Activities can occur any time after coaching session 4, within approximately 3 months of Baseline.

*After completion of coaching intervention, ideally the first prescriber appointment that follows the intervention (time frame could vary).

**Practice with Virtual Provider Program will be encouraged through the end of the study.

We anticipate each subject's participation to last approximately 3-4 months; however, this is dependent on when their first prescriber appointment following the intervention takes place.

The goal is to complete 4 weekly coaching sessions with each subject and the first session taking place within approximately 10 days of baseline data collection. We recognize the need to be flexible with the remaining sessions and will allow coaching sessions 2-4 to take place up to approximately 14 days after the previous session barring extenuating circumstances.

6.0 Data Management and Analysis Plan

Data Management and Quality Control. The Project Manager and RAs will create and maintain all databases. To ensure quality, data will be entered by one team member and checked by another. For qualitative data, transcribed interviews and coaching sessions will be checked for accuracy, de-identified, and entered in Atlas.ti or other appropriate qualitative data analysis program. The Project Manager and RAs, supervised by [name], will be responsible for data management. Each patient will be assigned an ID number, and all data will be entered into a database stored behind the University firewall on a secure, HIPAA-compliant server with limited access to appropriate IU research team members.

Data Analysis. Because inspection of the variable distributions is important for multivariate statistics, univariate and multivariate outliers, histograms, probability plots, and residual plots will be examined. We will also check the homogeneity of variances/covariances assumption by determining whether the correlations of the outcome measures with the covariates and their intercorrelations are approximately the same over time. Once we confirm the required assumptions for multivariate statistics, paired Hotelling's T-square test will be used to examine the mean differences of outcomes between baseline and post-intervention. Paired Hotelling's T-square test is used to account for the effect of correlations when there is more than one outcome variable. If the omnibus test rejects the null hypothesis, post-hoc tests will be conducted using the "partial" Bonferroni correction for potential family-wise type I error rates, which incorporates the mean correlation among dependent variables, because the traditional Bonferroni would be too conservative in our correlated data.¹²⁰

Power and sample size. This is a pilot study to test the feasibility and acceptability of GET PrEPD-Psychiatry. The primary purpose is not to conduct inferential statistical testing based on p-values.¹²¹ Nonetheless, we conducted a power analysis given the sample size we plan to obtain in order to facilitate our interpretation of the study findings. We are recruiting up to 40 subjects, and we expect minimal attrition based on our prior experience working with patients in this clinical setting – thus, our primary power analysis was based on a sample size of 40. Nevertheless, we also calculated power for a conservative estimate of 30 participants to account for potential loss to follow-up. Basing power on our two target mechanisms (patient activation and communication self-efficacy), G*Power 3.0.10 indicated that our study will have .64 to .78 power for the paired Hotelling's T-square test with a sample size of 30 to 40 (.05 alpha, $D^2=.5$ [medium effect size], two measures).

Missing data analysis. We anticipate some missing data, including study dropouts. We will compare patient demographic characteristics as well as baseline outcomes between those who withdraw and those who are retained to identify characteristics that discriminate dropouts. Further, we will carefully track study participation and try to understand reasons for dropout (and missing data) wherever possible. Identifying potential dropout (and missing data) mechanisms in this pilot study will allow us to incorporate those factors as auxiliary variables for multiple imputation as well as full information maximum likelihood estimation method assuming Missing At Random in our future full trial.

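### The stated power (.64 to .78) does not follow from the stated effect size: D²=.5 gives .92 to .98, and the printed powers match D²=.25

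*Combined protocol and SAP*

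**What the plan says.** Section 6.0, under Data Analysis, specifies the test: "paired Hotelling's T-square test will be used to examine the mean differences of outcomes between baseline and post-intervention". Under Power and sample size, the calculation is limited to two outcomes ("Basing power on our two target mechanisms (patient activation and communication self-efficacy"). The result reads "our study will have .64 to .78 power for the paired Hotelling's T-square test with a sample size of 30 to 40", with the inputs given as "05 alpha, $D^2=.5$ [medium effect size], two measures". Forty is the main case ("our primary power analysis was based on a sample size of 40"), and 30 allows for loss to follow-up.

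The same paragraph sets the role of the calculation. It says of the study that "The primary purpose is not to conduct inferential statistical testing based on p-values", and that power was nevertheless computed "in order to facilitate our interpretation of the study findings". D² is not defined there or anywhere else in the document, and no standard deviations, correlations or per-measure effects are given behind it.

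**The concern.** The sentence gives everything needed to compute the power of this test: the number of measures, alpha, the effect size and the sample size. Because D² already absorbs the variances and the correlation of the change scores, nothing is left to assume. The printed power should therefore follow from the printed D², and it looks far too low for it.

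This is the plan's only power statement, and its declared purpose is to help interpret the results. Taken as printed, it tells a reader that a true effect of D²=.5 would be missed 22% to 36% of the time (1 − .78 and 1 − .64). If that is wrong, a non-significant omnibus test could be put down to low power against an effect the study would almost certainly have detected. Anyone who carries the D² and the power together into planning a later trial would also start from a mismatched pair.

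**Working it through.** **Inputs, all from Section 6.0:** one group measured twice, so the test is a one-sample T-square on the change scores; p = 2 measures; alpha = .05; D² = .5; n = 30 and 40; stated power .64 and .78. The omnibus test has no sidedness to choose.

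**Formula.** Taking D² as the squared standardised (Mahalanobis) distance of the mean change vector from zero, T²·(n − p)/[p(n − 1)] follows a noncentral F distribution with p and n − p degrees of freedom and noncentrality λ = n·D². Power is the probability that it exceeds the central F 95th percentile.

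**Step 1: try to reproduce the plan's figure at D² = .5.**

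| n | df | critical F | λ = n × .5 | power | plan |
|---|---|---|---|---|---|
| 30 | 2, 28 | 3.340 | 15 | .917 | .64 |
| 40 | 2, 38 | 3.245 | 20 | .977 | .78 |

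It does not reproduce. The gaps are .92 − .64 = .28 and .98 − .78 = .20. A simulation of the test itself (40,000 runs per case) gives .919 and .978.

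**Step 2: find the D² that does reproduce it.** At D² = .25, λ is 7.5 and 10, and power is .637 and .782, which round to .64 and .78 (simulation: .639 and .786). Solving backwards:

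- Power that rounds to .64 at n = 30 needs D² of .2489 to .2543.
- Power that rounds to .78 at n = 40 needs D² of .2461 to .2519.
- The overlap is about .249 to .252.

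Both printed powers therefore point to the same value, .25 = .5², and rounding cannot bridge the gap to .5.

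**Step 3: look for another reading under which D² = .5 is right.** Power at n = 30 / n = 40:

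| Variant at D² = .5 | Power |
|---|---|
| λ = (n − 1)D² | .908 / .974 |
| λ = (n − 2)D² | .897 / .971 |
| three measures | .870 / .959 |
| four measures | .821 / .937 |
| five measures | .772 / .912 |
| alpha .025 | .857 / .954 |
| alpha .01 | .751 / .905 |
| chi-square approximation | .944 / .985 |
| two groups, n as total | .355 / .470 |
| two groups, n per group | .663 / .799 |

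None gives .64 and .78. The closest is the last, but it misses both figures and would need 60 to 80 participants in two arms. The plan has one arm and at most 40 participants.

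**Step 4: what the two effect sizes mean in participants.** At D² = .5, power first reaches .64 at n = 17 (.651), .78 at n = 22 (.791) and .80 at n = 23 (.813). At D² = .25, 80% power first comes at n = 42 (.804), just above the planned maximum. The D² detectable with 80% power is .36 at n = 30 and .26 at n = 40.

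**The case against.** The arithmetic is not in dispute; the case on the other side is about consequence and cause. If the unsquared D was used and simply printed as D², both powers are right for the calculation that was run and the defect is one superscript. A reader who relies on the medium-effect label and the powers would not be misled about that calculation. If D²=.5 was truly intended, the plan understates its power, which errs on the cautious side. The sample size was fixed before power was computed, the feasibility and acceptability aims do not use it, and the plan disclaims p-value testing as its main purpose.

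The cause is also unproven. If each of the two measures changes by d=.5, D² = 2 × .25/(1 + r), where r is the correlation of the change scores. This is .50 at r=0 and approaches .25 as r approaches 1, so D²=.5 is a coherent medium effect and the powers could be the wrong part. A formula misread from the PDF cannot be fully excluded either, though nothing points to one.

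Most of this stands as a limit on severity, and it means the gap of 28 and 20 points applies only if D²=.5 was intended. It does not remove the contradiction. The correlation affects how per-measure effects translate into D², but the plan states D² itself. On either reading the sentence is wrong as written.

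**Conclusion.** The concern holds. At alpha .05 with two measures, D²=.5 gives power of .92 at n=30 and .98 at n=40, against the stated .64 and .78. The stated powers belong to D²=.25, half the printed value. With D²=.5 the chance of missing the effect is 2% to 8%, where the printed powers imply 22% to 36%.

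This rests on D² having its usual meaning for the paired test and on the formula having been read correctly from the PDF. That D was printed as D² is an inference from the match at both sample sizes; the document alone does not show which effect was intended. The consequence is confined to how a null or positive T-square result is interpreted. It should be fixed because that is the declared use of the calculation.

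**What to change.** Check the saved software input, confirm the intended effect size, and restate the sentence in Section 6.0 in one of two ways:

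- power of .64 (n=30) to .78 (n=40) at D=.5, that is D²=.25; or
- power of .92 (n=30) to .98 (n=40) at D²=.5.

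Define D² in the same sentence as the squared standardised distance of the mean change vector from zero. Optionally, add the D² detectable with 80% power: .36 at n=30 and .26 at n=40.

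The cost is one sentence. The sample size, the analysis method and the conduct of the study are unchanged.

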7.0 Reportable Events, Suicidality Assessment

Adverse events will not be systematically collected from subjects. If a research team member becomes aware of any adverse events possibly related to study procedures, they will be reported to the Indiana University (IU) IRB according to the IU Standard Operating Procedures for Research Involving Human Subjects. Any unanticipated problems involving risk to participants or others will also be reported according to the IU Standard Operating Procedures for Research Involving Human Subjects.

Because this is a study to develop a shared decision-making intervention, and we are not targeting depression or suicide (or assessing either as a study outcome), we will not directly assess suicidal thoughts. However, we recognize that the topic of suicide may come up during a coaching session or during a data collection interview. If a participant describes having current thoughts of suicide, hopelessness, or feeling as though they would be better off dead during a research activity (either a coaching session or a data collection event), the research assistant will proceed to a scripted brief interview (Patient Suicidality Form) to assess risk. If a participant is considered high risk (patient answers "yes" to questions 1 and/or 2 on the form), procedures are immediately employed by connecting the participant with a qualified mental health professional at SEMHC during an in-person visit. SEMHC is a mental health facility that employs psychiatrists, clinical psychologists, nurses, and social workers who are qualified and capable of assessing and treating suicidality. In our other studies with Eskenazi Health, we have established a similar referral protocol so that participants who express suicidal ideation are connected with a clinician during the visit, while onsite. If a patient is assessed to be high risk for suicidality during a phone or video call (using the Patient Suicidality Form), the research assistant will connect the patient with the Sandra Eskenazi Mental Health Center crisis line and/or other appropriate community resource (e.g., emergency department, national suicide hotline). The research assistant will also inform appropriate treatment team staff at SEMHC as soon as possible. In addition, the research assistant will inform either [name], [name], or [name] (all are Clinical Psychologists) as well as the project manager immediately following the visit so that it can be ensured that effective safety procedures were followed and appropriate reporting is completed.

8.0 Summary

This project addresses the **significant** public health issues of providing patient-centered care to enhance self-management and recovery outcomes for people with SMI. As a developmental R34, we are taking the critical first step in assessing feasibility and acceptability of an innovative and scalable approach that has the potential to efficiently and substantially shift care. GET PrEPD-Psychiatry is characterized by key **innovations**. Our intervention explicitly focuses on patient-level target mechanisms that facilitate self-management and

collaborative care. Moreover, the innovative practice sessions with Virtual Providers are tailored to the learning needs/preferences of individual patients and allow for frequent skills practice, leading to skills mastery and patient self-efficacy. Our **approach**, informed by our extensive prior work, is scientifically rigorous and pragmatic. GET PrEPD-Psychiatry will yield new and important knowledge about collaborative care for people with SMI and will be ready for wide dissemination in a variety of clinical settings. The **investigators'** expertise, track record, and history of collaborating on funded and published research provide strong evidence of our ability to complete this project. The **scientific and clinical environments** are optimal, and there is considerable institutional support for the study team. In summary, **successful completion of this project** will result in a new, highly scalable intervention that can be implemented across a range of settings to reach a large number of patients, thus having a positive and sustained impact on mental health research and care.

Bibliography and References Cited from Grant Proposal

3. Deegan PE. The importance of personal medicine: A qualitative study of resilience in people with psychiatric disabilities. *Scandinavian Journal of Public Health*. 2005;33(66 suppl):29-35.
